9.5.2.2 Cardiovascular Risk Factors Biomarker of Exposure

Summary of Cardiovascular Risk Factors		
Population	:	FAS
Group	:	
• Study Arm• Product Use Category
Contents	:	
• Refer to Descriptive statistics• Calculate the value of Cardiovascular Risk Factors for each visit. Also, calculate the change from baseline.
Analysis variables	:	
• Systolic blood pressure• Diastolic blood pressure• Body weight• Waist circumference
Target visit		Baseline (V2) to V8
Output		Summary of Cardiovascular Risk Factors -FAS- Summary of Cardiovascular Risk Factors by Product Use Category - FAS- Series plot of Cardiovascular Risk Factors -FAS- Series plot of Cardiovascular Risk Factors by Product Use Category - FAS- Listing of Cardiovascular Risk Factors

Summary Table of Analysis for BoExp Geometric Mean Value		
Population	:	FAS
Group	:	
• Study Arm• Product Use Category
	:	
• The analysis will be performed on the FAS using a mixed model for repeated measurements (MMRM).• The model will include the log transformed BoExp adjusted for creatinine as the dependent variable, adjusting for the following covariates;

Confidentiality Statement

Data and information contained in this document are considered to constitute trade secrets and confidential commercial information, and the legal protections provided to such trade secrets and confidential information are hereby claimed under the provisions of applicable law. No part of this document may be publicly disclosed without the written consent of Philip Morris Products S.A

Summary Table of Analysis for BoExp Geometric Mean Value

	
➤ Study Arm or Product Use Category➤ log(BoExp value at V2)➤ Visit➤ Interaction between visit and Study Arm or Product Use Category• Degree of freedom will be adjusted by using KR.• Number of patients included in analysis, Geometric LS means (IQOS-CIG), Ratio of Geometric LS Means and 95% CI for Ratio of Geometric LS means at each visit for each product use will be presented.• Select Unstructured (UN) specified for the correlation structure. If the model fails to converge try following option in order; a first order autoregressive (AR(1)), Compound Symmetry (CS), and uncorrelated (IND).
Analysis variables	
• NEQ adjusted for creatinine• Total NNAL adjusted for creatinine• Total NNN adjusted for creatinine• 2-CyEMA adjusted for creatinine
Target visit	: V3 to V8
Sample code	<pre>proc mixed data=test ; class ARM VISIT ; model Log(AVAL) = ARM Log(Base) VISIT ARM * VISIT / s cl ddfm=kr; repeated VISIT / type=un subject=USUBJID ; lsmeans ARM * VISIT / diff=control("CIG" "1") cl ; ods output diffs=diff ; ods output lsmeans=lsmean ; ods output convergencestatus=check ; run;</pre>
Output	Summary of Analysis for BoExp Geometric Mean Value -FAS- Summary of Analysis for BoExp Geometric Mean Value by Product Use Category -FAS-

Confidentiality Statement

Data and information contained in this document are considered to constitute trade secrets and confidential commercial information, and the legal protections provided to such trade secrets and confidential information are hereby claimed under the provisions of applicable law. No part of this document may be publicly disclosed without the written consent of Philip Morris Products S.A.

Summary Table of Analysis for BoExp Geometric Mean Value

	
Time Series Plot of Geometric LS Mean Biomarkers of Exposure Parameters -FAS-
 
Time Series Plot of Geometric LS Mean Biomarkers of Exposure Parameters by Product Use Category -FAS-
 
Listing of Statistical Output (MIXED procedure)
 
Listing of Statistical Output (MIXED procedure) by Product Use Category

--	---

Summary Table of BoExp Parameters

Population	:	FAS
Group	:	
• Study Arm• Product Use Category
Contents	:	In addition to the descriptive statistics of value and change from baseline for each visit, the number and percentage of values below LLOQ or above ULOQ will be presented. If more than 50% of the data are below LLOQ, only the number and percentage of values below LLOQ will be reported in the summary together with the minimum and maximum values. In addition, the geometric means, CV and geometric relative change will be presented.
Analysis variables	:	
• NEQ adjusted for creatinine• Total NNAL adjusted for creatinine• Total NNN adjusted for creatinine• 2-CyEMA adjusted for creatinine• Creatinine (Only on listing)
Target visit		Baseline (V2) to V8
Output		Summary of Biomarkers of Exposure Parameters -FAS- Summary of Biomarkers of Exposure Parameters by Product Use Category -FAS- Listing of Biomarkers of Exposure Parameters

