7.6.1 Biomarker of Exposure

7.6.1.1 Total NNAL, Total NNN, CEMA, and NEQ in Urine

At V2 to V8: spot urine collection to measure biomarkers of exposure (expressed as concentration adjusted to creatinine):

- total NNAL, a biomarker for NNK (4-(methylnitrosamino)-1-(3-pyridyl)-1-butanone),
- total NNN, a biomarker for NNN (N-nitrosonornicotine),
- CEMA, a biomarker for acrylonitrile, and
- NEQ, a biomarker to nicotine.

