12.3 Product Use

Although patients are being requested to use solely the product allocated to their respective study arm, it is considered that not all patients randomized to the IQOS arm or to continue smoking CC will exclusively use the randomized product at all times during the study. For instance, patients may concomitantly use IQOS and CC (dual use). Similarly, it is expected that some patients in the SC arm who had stopped smoking after AAA diagnosis may relapse to the use of tobacco or nicotine-containing products (e.g., CC or IQOS). Those patients who might change their smoking habits after randomization to an arm (e.g., who have been allocated to the IQOS arm but restart smoking CC) will remain for the statistical analysis in the arm they have been randomized to.

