12.7 Secondary Analysis

Descriptive statistics for the maximum minor-axis AAA diameter will be summarized at each visit and overall (across all patients). The endpoints will also be summarized by strata (maximum-minor-axis AAA diameter, CC consumption, sex).

Urinary NEQ, and Total NNAL, Total NNN, and CEMA levels (concentration data adjusted for creatinine will be analyzed on a logarithmic scale) using an MMRM with the logarithmic transformation.

Descriptive statistics for the secondary endpoints shown below, will be summarized at each visit, except for vital signs (systolic and diastolic blood pressure) which will be summarized

Confidentiality Statement

Data and information contained in this document are considered to constitute trade secrets and confidential commercial information, and the legal protections provided to such trade secrets and confidential information are hereby claimed under the applicable provisions of applicable law. No part of this document may be publicly disclosed without the written consent of Philip Morris Products S.A.

every 12 months, by exposure group and overall (across all patients) in the FAS (unless otherwise defined):

- Time from diagnosis of AAA until open surgical AAA treatment or endovascular repair
- Time from diagnosis of AAA until AAA rupture
- Annual growth rate of AAA
- Nicotine equivalents (NEQ): molar sum of free nicotine, nicotine-glucuronide, free cotinine, cotinine-glucuronide, free trans-3'-hydroxycotinine, trans-3'-hydroxycotinine-glucuronide in spot urine (expressed as concentration adjusted to creatinine)
- Systolic and diastolic BP
- Body weight and waist circumference

For the secondary endpoints shown below, the number at each visit and overall (across all patients) will be described:

- Number of patients with open surgical AAA treatment or endovascular repair annually (based on date of decision to perform open surgical AAA treatment or AAA endovascular repair)
- Number of patients with a AAA rupture annually (based on date of AAA rupture)
- Number of patients with an increase in maximum minor-axis AAA diameter of more than 5 mm within 6 months
- Number of patients with an overall maximum minor-axis AAA diameter >55mm in male patients and >50mm in female patients
-
- Incidence of IQOS malfunctions and misuses
- Number of tobacco products used, (including CC and HeatSticks) based on self-reporting

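### Biomarker MMRM: the SAP text asks for the IQOS/CIG ratio at each visit, but the sample code compares every cell with one fixed CIG cell and prints at most one of the six same-visit ratios per biomarker

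*SAP*

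**What the plan says.** SAP 9.5.2.2 (Summary Table of Analysis for BoExp Geometric Mean Value) plans a repeated-measures model on log creatinine-adjusted biomarkers. The covariates are group, log V2 value, visit and the group-by-visit interaction. The stated results include "Geometric LS means (IQOS-CIG), Ratio of Geometric LS Means and 95% CI for Ratio of Geometric LS means at each visit". The target visits are V3 to V8. The analysis covers four biomarkers (NEQ, Total NNAL, Total NNN, 2-CyEMA) and is done twice, by study arm and by product use category.

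The sample code fits "model Log(AVAL) = ARM Log(Base) VISIT ARM * VISIT / s cl ddfm=kr", then requests "lsmeans ARM * VISIT / diff=control('CIG' '1') cl" and saves the result through "ods output diffs=diff". The LS means are saved too. There is no slice by visit, no ESTIMATE statement, and no wording that the comparator moves with the visit. The planned outputs include a "Listing of Statistical Output (MIXED procedure") for each grouping.

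Protocol 12.7 says only that these biomarkers are analysed "using an MMRM with the logarithmic transformation", so it does not settle which contrasts are meant.

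**The concern.** The difference option names a single cell, CIG at visit 1, as the reference for all other cells. A ratio at each visit needs the reference to be CIG at that same visit. The text and the code therefore specify different contrasts, and nothing in the SAP says which prevails.

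The later-visit IQOS rows would look like visit-specific ratios but would use a V3 denominator. A programmer or reader who took such a row as the ratio at V8 would absorb any change in CIG exposure since V3 into the apparent product effect. This is the one model-based comparison of exposure between the two randomised arms, so the contrast should be unambiguous.

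**Working it through.** **Inputs.** Three arms (SAP 4.1), five product use categories (SAP 5.7), six target visits and four biomarkers (SAP 9.5.2.2). The plan states no figure to reproduce, so the check is a count of the rows that the code prints.

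**Study-arm version, visits recoded so that 1 = V3.**
- Cells: 3 × 6 = 18. Differences from one fixed cell: 18 − 1 = 17.
- These are 6 IQOS rows, 6 SC rows and 5 CIG rows (CIG later against CIG at V3).
- Same-visit rows: 2, namely IQOS/CIG at V3 and SC/CIG at V3. So 1 of the 6 required IQOS/CIG ratios is printed.

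**Product-use version, same coding, all categories populated.** Cells: 5 × 6 = 30; differences: 29; same-visit rows: 4, of which 1 is IQOS/CIG. Again 1 of 6.

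**Visits labelled V3 to V8.** The cell CIG at visit 1 does not exist, so none of the six is printed. Reading 1 as V1 does not help: Protocol 7.6.1.1 has "At V2 to V8: spot urine collection to measure biomarkers of exposure", so there is no biomarker value at V1.

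**Totals.** Planned: 4 biomarkers × 6 visits = 24 ratios per grouping, 48 over both (if the IQOS and CIG categories both contain patients). Printed directly: 4 + 4 = 8 of 48, or 0 of 48.

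**What the other five IQOS rows mean.** On the ratio scale, for visit j:

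IQOS(j) / CIG(V3) = [IQOS(j) / CIG(j)] × [CIG(j) / CIG(V3)].

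The discrepancy is exactly the CIG change since V3. For an assumed same-visit ratio of 0.50, if CIG at V8 is 1.0, 0.9, 0.8 or 0.7 times its V3 level, the V8 row reads 0.50, 0.45, 0.40 or 0.35.

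**Could the CIG arm drift?** In the study-arm version, yes. Patients who change habits "will remain for the statistical analysis in the arm they have been randomized to" (Protocol 12.3), and Protocol 7.2 encourages quitting throughout. Assume 11 CIG patients, since the documents give 32 enrolled (Protocol 4.4) but no split. If k of them stop and exposure falls R-fold, the geometric mean falls by 1 − R^(−k/11). That is 6% for k = 1, R = 2 and 34% for k = 2, R = 10. 

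**Scale against precision.** With an assumed 11 per arm and log-scale SD of 0.7, ignoring covariate adjustment, the half-width of a same-visit 95% CI is t(20) × 0.7 × √(2/11) = 2.086 × 0.7 × 0.426 = 0.62. This is a factor of exp(0.62) = 1.86 each way. A 10% CIG decline moves the row by −ln(0.9)/0.62 = 17% of that half-width, and a 30% decline by −ln(0.7)/0.62 = 57%.

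**What can be rebuilt when 1 = V3.**
- Point ratio, on the log scale: [IQOS(j) − CIG(V3)] − [CIG(j) − CIG(V3)] = IQOS(j) − CIG(j).
- Standard error: the saved LS-mean and difference standard errors give Cov(IQOS(j), CIG(V3)) = {Var IQOS(j) + Var CIG(V3) − Var[IQOS(j) − CIG(V3)]} / 2.
- Groups covary only through the shared baseline slope. With complete data, Cov(IQOS(j), CIG(j)) therefore equals that value exactly, and Var[IQOS(j) − CIG(j)] follows.
- I checked this by generalised least squares with known covariance. The rebuilt over true standard error was 1.000 with complete data. With assumed missingness (6% dropout per visit, or 10% intermittent), the central 95% of values was 0.99 to 1.01 and the extremes 0.96 to 1.04. The contrast-specific Kenward-Roger degrees of freedom are not printed.

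**The case against.** The strongest reply is that the block is labelled sample code and is plainly a template. It writes log transforms inside the MODEL statement and shows only the arm version, although product use category is also planned. Other blocks are as loose: the Kaplan-Meier sample in SAP 9.5.2.1.1 shows numbers at risk to 18 months, while its text wants estimates to 36. The text states the right quantity, and the table layouts sit in a separate shell document. No sentence says that the fixed-cell rows feed the summary table. If visits keep their labels, the named control does not exist, so no wrong ratio could be reported.

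Most of this stands, and it limits the point to a mismatch to correct. It does not remove it. The SAP has no rule that text overrides code, and the listing of model output is itself a planned product.

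A reader might go further and infer that the five later-visit confidence intervals are lost. The documents do not support that: the code saves both LS means and differences, from which the standard errors follow exactly with complete data and closely otherwise. A reader might also apply the quitting illustration to both groupings. It does not carry over, because the CIG product use category in SAP 5.7 requires an average of at least one cigarette per day at every visit from V3 to V8. A patient who stops is classified elsewhere.

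**Conclusion.** The point holds as a code-versus-text error. Followed literally, the sample code prints 1 of 6 same-visit IQOS/CIG ratios per biomarker (8 of 48 over both groupings) if 1 means V3, and none if visits are labelled V3 to V8. These counts need no assumption beyond the visit coding and populated categories.

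The numerical consequence is conditional. It arises only if a later-visit row is read as a same-visit ratio, and it equals the CIG change since V3. With no such change the point estimate is unaffected. The drift, arm size and SD used above are assumptions.

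A reader might infer that the model is wrong or that the trial's main result is at risk. Neither follows. The fitted model can supply the intended ratios, and the primary growth-rate analysis does not use this code. The study is descriptive, with no hypothesis tests (SAP 3.5.1). The correction is still worth making, because a planned listing would otherwise carry contrasts that the text did not ask for.

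**What to change.** - Replace the LSMEANS difference option with same-visit contrasts against CIG at each of V3 to V8. Either six ESTIMATE or LSMESTIMATE statements, or all pairwise group-by-visit differences filtered to equal visit, will do. This gives 6 of 6 ratios with 95% CI per biomarker, 24 of 24 per grouping.
- Do the same in the product-use-category version.
- Use visit labels that exist in the analysis data.
- Add one sentence to the SAP saying that the text governs where sample code differs.

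The cost is SAP wording and code only. No new data are needed and the model does not change. If the SAP can no longer be amended before database lock, SAP section 1 already provides for describing such a change in the study report.

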9.5.3 Additional Analyses

Summary of ABI (Ankle-Brachial Index)		
Population	:	FAS
Group	:	
• Study Arm• Product Use Category
Analysis variable	:	For Left Ankle-Brachial Index and Right Ankle-Brachial Index, count the number of subjects by visits in the category shown. <0.9 $0.9 <= <1.0$ $1.0 <=$
Output	:	Summary of Ankle-brachial Index -Safety Set- Summary of Ankle-brachial Index by Product Use Category -Safety Set- Listing of Ankle-brachial Index

Summary of CREs (Clinical Risk Endpoints)		
Population	:	FAS
Group	:	
• Study Arm• Product Use Category
Analysis variable	:	
• Refer to Descriptive statistics• Calculate the value of CREs for each visit. Also, calculate the change from baseline. TC, TG, fasting blood glucose, WBC, and platelet counts are summarized in “9.5.4.3 Clinical Laboratory Evaluation”
Output	:	Summary of CREs -FAS- Summary of CREs by Product Use Category -FAS- Listing of CREs

Confidentiality Statement

Data and information contained in this document are considered to constitute trade secrets and confidential commercial information, and the legal protections provided to such trade secrets and confidential information are hereby claimed under the provisions of applicable law. No part of this document may be publicly disclosed without the written consent of Philip Morris Products S.A

Summary of Co-morbidities		
Population	:	FAS
Group	:	
• Study Arm• Product Use Category
Contents		
• The number and percentage of patients with co-morbidity and the terms of co-morbidity will be calculated.• Co-morbidity terms:
➢ Ischemic Heart Disease (IHD)➢ Progression of IHD
✧ Progression of IHD: Myocardial infarction✧ Progression of IHD: Stroke➢ Chronic Obstructive Pulmonary Disease (COPD)➢ Progression of COPD➢ Hypertension➢ Progression of hypertension➢ Peripheral Arterial Disease (PAD)➢ Progression of PAD
Output	:	Summary of Co-morbidities -FAS- Summary of Co-morbidities by Product Use Category -FAS- Listing of Co-morbidities

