3.4 Additional Endpoints

Throughout the course of the study, several amendments to the protocol were issued with updates on some of the objectives or endpoints considered. The following endpoints have been collected up to the issuances of these amendments (note that subjects were enrolled only after protocol version 4 was issued):

Amendments	Endpoint
Protocol version 6	
Part of the Selected clinical risk endpoints (CREs) in Secondary Objectives and Endpoints are collected up to the amendments.
 
• Hemoglobin A1c (HbA1c)• Total Antioxidant Capacity (TAC)• Metalloproteinase (MMP) 2 and 9
Protocol version 7	
Secondary Objectives and Endpoints below are collected up to the amendments.
 
• Co-morbidities• CREs
◦ High sensitive C-reactive protein (hs-CRP)◦ Low density lipoprotein (LDL)◦ High density lipoprotein (HDL)◦ Total Cholesterol (TC)*◦ Triglyceride (TG)*◦ Fasting blood glucose*◦ White blood cell (WBC)*◦ Platelet counts*◦ D-dimer◦ Fibrinogen◦ 11-dehydro-thromboxane B2 (11-DTX-B2)◦ 8-Epi Prostaglandin F2 Alpha (8-epi-PGF_{2α})◦ Soluble inter-cellular adhesion molecule-1 (sICAM-1)◦ Apolipoprotein A1 (Apo A1)◦ Apolipoprotein B (Apo B)◦ Homocysteine in the respective body matrix• Ankle-brachial index (ABI)• Assessment of Transcriptomic, Proteomic, and Lipidomic Profiles
◦ Transcriptomic, proteomic and lipidomic profiles assessment derived from blood samples◦ Lipidomic profile assessment in urine

Confidentiality Statement

Data and information contained in this document are considered to constitute trade secrets and confidential commercial information, and the legal protections provided to such trade secrets and confidential information are hereby claimed under the provisions of applicable law. No part of this document may be publicly disclosed without the written consent of Philip Morris Products S.A.

The data related to these endpoints will be listed and summarized in AAA patients who switch from smoking CIG to using IQOS, patients who continue to smoke CIG, and patients who had stopped smoking.

* Note that TC, TG, fasting blood glucose, WBC, and platelet counts are still part of the objective related to safety monitoring. These will be analyzed as part of that objective and not considered here as additional endpoints.

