5.6 ABI (Ankle-Brachial Index)

Items (left and right)	Units
Calculated ABI	-
Systolic pressure at the dorsalis pedis artery	mmHg
Systolic pressure at the posterior tibial artery	mmHg
Brachial arterial systolic pressure	mmHg

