9.1.3 Descriptive Statistics

Data will be presented in listings, enrollment arm, patient, and study visit, unless otherwise specified.

For continuous data, summary statistics will include the number of patients with non-missing values [n], number and percent of patients with missing data, the mean and standard deviation (SD), median, first and third quartiles, minimum and maximum, and 95% confidence interval (CI). Log-normally distributed data (e.g., BoExp data) will also include the geometric mean and coefficient of variation (CV) in addition to the mean and SD. Post-baseline summaries will include change from baseline apart from log-normal variables which will present % change from baseline (see Section 5.1.2).

Confidentiality Statement

Data and information contained in this document are considered to constitute trade secrets and confidential commercial information, and the legal protections provided to such trade secrets and confidential information are hereby claimed under the provisions of applicable law. No part of this document may be publicly disclosed without the written consent of Philip Morris Products S.A.

For categorical data, frequency counts and percentages will be presented. Percentages of missing values will be computed using the number of patients [N] included in the corresponding group in the denominator, while percentages related to ‘non-missing’ categories will be computed using the number of patients with non-missing values in the denominator.

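### SAP 9.5.3 summarises ankle-brachial index, a continuous measure, only as counts in three bands, without the descriptive statistics and change from baseline that SAP 9.1.3 sets for continuous data

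*SAP*

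**What the plan says.** SAP 5.6 lists "Calculated ABI" for left and right, together with the dorsalis pedis, posterior tibial and brachial pressures in mmHg. These are numeric variables.

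The ABI box in SAP 9.5.3 then reads: "For Left Ankle-Brachial Index and Right Ankle-Brachial Index, count the number of subjects by visits in the category shown". Three categories follow: below 0.9, 0.9 to below 1.0, and 1.0 or above. Results are grouped by study arm and, separately, by product use category. The planned outputs are those two summaries and a "Listing of Ankle-brachial Index". The box does not refer to the descriptive statistics and has no line on change from baseline.

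The next box, on clinical risk endpoints (CREs), refers to the descriptive statistics and adds: "Calculate the value of CREs for each visit. Also, calculate the change from baseline".

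The general rule is in SAP 9.1.3. Continuous data receive n, missing counts, mean, SD, median, quartiles, range and a 95% CI. It continues: "Post-baseline summaries will include change from baseline apart from log-normal variables", with percent change used for the log-normal ones.

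SAP 3.4 places ABI among the additional endpoints that were collected up to an amendment (the protocol version 7 row). It says of them: "The data related to these endpoints will be listed and summarized in AAA patients".

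**The concern.** A variable held on a continuous scale reaches the reader of the planned tables only as three counts per leg, group and visit. Two things are lost.

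- **Position within a band.** Every value of 1.0 or above is treated as the same. A patient who falls from 1.3 to 1.0 appears unchanged.
- **Within-patient change.** The counts at each visit are marginal. If one patient moves up a band and another moves down, the table does not change. No shift table or change score is planned.

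The SAP gives no reason for treating ABI differently from the CREs. Of the other additional endpoints in SAP 3.4, co-morbidities are categorical, and SAP section 7 says the transcriptomic, proteomic and lipidomic profiles will not be evaluated. ABI is therefore the only numeric additional endpoint with a summary table that omits the SAP 9.1.3 statistics. In a study without hypothesis tests, the descriptive tables are the result, so what they leave out matters more than it would elsewhere.

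**Working it through.** The documents state no precision, power or sample size for ABI, so there is no plan figure to reproduce. The check is how much information on a mean survives the banding.

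**Inputs from the documents.** Cut-points 0.9 and 1.0 (SAP 9.5.3). 32 enrolled of 114 planned, with 15 more forecast as potentially eligible before recruitment was stopped early (Protocol 4.4). IQOS and cigarette arms randomised 1:1; smoking cessation arm not randomised and of unstated size (Protocol 6.4).

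**Assumptions, not in the documents.** ABI is roughly normal with mean 1.00 to 1.10 and SD 0.10 to 0.15. About 11 patients per arm: 32/3 = 10.7, which needs three equal arms and enrolment ending at 32. With all 15 forecast patients it would be 47/3 = 15.7.

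**Formula.** For a normal variable grouped into bands with standardised limits l and u and band probability p, the share of the Fisher information on the mean that is kept is the sum over bands of (φ(l) − φ(u))² / p.

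**Worked case: mean 1.05, SD 0.10.** The limits are (0.9 − 1.05)/0.10 = −1.5 and (1.0 − 1.05)/0.10 = −0.5.

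- Below 0.9: p = 0.067, and 0.1295² / 0.0668 = 0.251
- 0.9 to below 1.0: p = 0.242, and (0.1295 − 0.3521)² / 0.2417 = 0.205
- 1.0 or above: p = 0.691, and 0.3521² / 0.6915 = 0.179
- Sum: 0.64 kept, so 36% lost

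**Full assumed grid.**

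| Mean | SD | Share in the three bands | Kept | Lost |
|---|---|---|---|---|
| 1.00 | 0.10 | 16 / 34 / 50% | 76% | 24% |
| 1.00 | 0.15 | 25 / 25 / 50% | 75% | 25% |
| 1.05 | 0.10 | 7 / 24 / 69% | 64% | 36% |
| 1.05 | 0.15 | 16 / 21 / 63% | 68% | 32% |
| 1.10 | 0.10 | 2 / 14 / 84% | 46% | 54% |
| 1.10 | 0.15 | 9 / 16 / 75% | 58% | 42% |

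At 11 per arm, 46% to 76% kept is equivalent to about 5 to 8 patients measured on the full scale. More than half is lost in one of the six cases.

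**Outside the grid.** With SD between 0.08 and 0.20, the bands keep 73% to 81% at a mean of 0.90 to 1.00, but only 5% to 46% at a mean of 1.20. The best possible three-band split of a normal variable keeps 81%.

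**What the added summary would show.** At 11 per arm, the 95% CI half-width for an arm mean is t(0.975, 10)/√11 = 2.228/3.317 = 0.67 SD, which is 0.07 to 0.10 ABI units for SD 0.10 to 0.15. For comparison, 2 patients of 11 in a band has an exact 95% CI of 2% to 52%, and the ABI box plans no interval for its counts.

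**The case against.** Several points on the other side have force.

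**The values are not lost.** A listing is planned, SAP section 1 allows additional analyses to be described in the study report, and the table shells are a separate document not seen here. This stands as far as it goes. But a listing is not a summary, and SAP 3.4 promises both. If SAP 9.1.3 is meant to apply by default, the ABI box does not say so and the CRE box does; one line would settle it.

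**A reader might infer that the bands discard most of the information, or that the table will be nearly all one cell.** The documents do not support this. They give no ABI distribution. Under the assumptions above most is lost in only one case of six, and at a mean of 1.00 half the patients fall below 1.0. The stronger statement needs a population sitting mostly above 1.0.

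**A reader might infer that the planned table says nothing about switching.** That is also too strong. IQOS and cigarettes are randomised, so banded counts by arm at a post-baseline visit do allow a comparison between those arms. What is missing is within-patient change.

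**The absence of a cited reason proves little.** ABI came from protocol versions that are not available, and any rationale for the cut-points may lie there.

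**The weight is low.** ABI is not among the current primary or secondary endpoints, and no hypothesis is tested. Because collection stopped at an amendment, few patients may have later values, which also limits what a change-from-baseline summary could show. This is fair, but the CREs stopped in the same way and still receive the full summary.

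**Conclusion.** The point holds as a gap in the ABI table. The box departs from the SAP's own rule for continuous data and from the adjacent box, with no stated reason, and it leaves within-patient change out of every planned summary. That conclusion comes from the text and needs no assumption.

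The size of the loss does need one. It is about 24% to 54% of the information on the mean for an assumed mean of 1.00 to 1.10 and SD of 0.10 to 0.15, and larger if the mean is higher. The figure of about 11 per arm is likewise an assumption (32 enrolled, three equal arms); numbers with post-baseline ABI may be smaller.

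The consequence for the trial is small. This is an inexpensive improvement to a secondary table and does not affect the primary analysis.

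**What to change.** In the ABI box of SAP 9.5.3, add the wording used for the CREs: the SAP 9.1.3 descriptive statistics with 95% CI, and change from baseline, for left and right ABI by group and visit. SAP 9.1.4 already defines baseline. Keep the three band counts as supplementary rows.

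While the box is open, reconcile its population: it names the FAS, but its summary outputs are labelled Safety Set.

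The cost is a line or two of SAP text and one more block in an existing table. No new data or derived variable is needed. If the SAP is already final, the summary can be added and described in the study report, as SAP section 1 allows.
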